### **Project Overview/Summary:**

**Title of study:** Taltz (ixekizumab) in the Treatment of Bullous Pemphigoid (BP)

**Purpose and rationale:** BP is the most common auto-immune blistering disease of the skin and causes significant morbidity. BP disproportionately affects the elderly population and the current, non-specific immunosuppressive therapies, in addition to patient comorbidities, are associated with a high risk of infection related mortality. (1) Neutrophils and their proteases have been shown to play a major role in the cleavage of Bullous Pemphigoid 180 Antigen (BP180) in BP. (2) Mast cells and other cellular mediators also contribute to the pro-inflammatory environment within and surrounding blisters of BP. (3) However, the prior targeting of mast cells and basophils has resulted in unpredictable disease control. (4) Recently, IL-17 has been identified as a key driver of chronic inflammation in BP. (5) With the increasing aged population in the United States, BP will increase in prevalence and the development of a more targeted approach will be necessary to decrease morbidity and mortality. IL-17 inhibition with Taltz (ixekizumab) may have targeted, disease-modifying effects on BP.

**Objectives:** The primary objective is to test the effect of Taltz (ixekizumab) in the treatment of the autoimmune blistering disease, BP. The effect will be accessed by the change in blister formation, bullous pemphigoid disease activity index (BPDAI) (6), and the total dose of prednisone while on therapy. The primary endpoint is the median time from first dose of Taltz (ixekizumab) to cessation of new blister formation. Secondary objectives include the examination serological markers of BP and correlation with disease activity and the safety of Taltz (ixekizumab) in BP patients.

**Population:** BP patients (treatment naïve and treatment refractory) meeting clinical, histological and immunologic criteria for the disease will be enrolled.

#### **Inclusion/Exclusion criteria:**

Inclusion: Non-pregnant adults with BP.

#### **Investigational and reference therapy:**

*Investigational:* Taltz (ixekizumab) 80mg subcutaneous (160mg week 0, then 80mg weeks 2, 4, 6, 8, 10, & 12)(7)

*Control (prior to washout):* Standard of care therapy prior to washout

*Rescue Therapy:* Prednisone (see [Supplement 4](#))

**Study design:** This is a single center, exploratory, open-label, single-arm design study of 12 patients. Treatment naïve and treatment refractory patients will be treated with Taltz (Ixekizumab). Patients who are non-responders, to physician choice standard of care, will undergo a washout period and will be enrolled in the study. The study consists of 3 epochs: screening/washout period (of at least 1 week and up to 4 weeks), treatment epoch (of 12 weeks from screen/washout), and follow up epoch (of 6 weeks). The screening and washout period will allow for treatment naïve/ new diagnosis BP to undergo evaluation and diagnosis and for treatment refractory to undergo a washout. The total duration of the study will be 18 weeks.

#### **Primary Endpoint:**

Median time from first dose of Taltz (ixekizumab) treatment to cessation of new blisters.

#### **Secondary Endpoints:**

Change in BPDAI (6) on Day 0 to Week 12

Total dose of prednisone required during each epoch

Changes in disease activity after discontinuation of Taltz (Ixekizumab) (week 12 to 18)

Clinical safety of Taltz (Ixekizumab)

#### **Data analysis:**

This study is exploratory in nature. We will access for the effects of Taltz (ixekizumab) on new blister formation as well, BDAI, and corticosteroid usage.

## **Introduction:**

Bullous Pemphigoid (BP) is an autoimmune blistering disease that affects the elderly population. Nearly 3,000 to 5,000 new cases of BP will be diagnosed in the United States each year. (8, 9) The incidence of BP has nearly doubled in the last decade. (9) The risk of BP increases significantly with age where individuals over the age of 90, relative to those 60 or younger, are at a 300 fold increased risk of developing BP. (8) BP is characterized clinically by: skin blistering, severe pruritus or itch, and a decreased quality of life. Due to increased life expectancy in the United States, the rates of BP will likely rise in the future.

The pathogenesis of BP is due to antibodies that target the 180kD and 230kD BP proteins, BPAG2 and BPAG1 respectively. BPAG2 is felt to be the key mediator of disease activity in BP. (10) Neutrophils and their proteases have been shown to play a critical role in the cleavage of BPAG2. (2) Mast cells and other cellular mediators also contribute to the pro-inflammatory environment within and surrounding blisters of BP. (3) However, the prior targeting of mast cells and basophils has resulted in unpredictable disease control. (4) The current treatment for BP is most commonly non-specific immunosuppression, which improves the morbidity but may contribute to sepsis related mortality. (1) One study found that nearly 56% percent of individuals with BP developed infection related complications. (1) The aim of therapy is to either decrease the levels of pathogenic antibody or to decrease the inflammatory response.

The current therapeutic hierarchy, based upon randomized controlled trials (RCTs), for BP is largely reliant upon oral (up to 0.75mg/kg of prednisolone or prednisone) and topical (up to 40g of clobetasol daily) corticosteroids as well as adjuvant steroid sparing agents (azathioprine or mycophenolate mofetil). (11-14) A slow taper of oral corticosteroids is considered first-line for disease requiring systemic therapy. Therefore, the use of prednisone as a rescue therapy will allow for the assessment of Taltz (Ixekezumab) as a steroid sparing agent. Non-RCT based immunosuppression with rituximab and methotrexate have also been reported to be successful. (15, 16) Non-immunosuppressive agents including doxycycline, tetracycline, and niacinamide are reported to improve disease; however, only tetracycline and niacinamide have been compared to immunosuppressive agents. (17) There is one ongoing trial comparing doxycycline to prednisone in BP. (18)

Recently, IL-17 has been identified as a key driver of chronic inflammation in BP. (5) IL-17 inhibition may provide a much needed and more targeted treatment, with a better side effect profile. Taltz (ixekizumab) is a recombinant high-affinity fully human monoclonal antibody that targets IL-17A IgG1/kappa-class. Taltz (ixekizumab) neutralizes IL-17A and targets the Th17 pathway, which has been clearly shown to be involved in the pathogenesis of psoriasis with unprecedented responses. (7) In addition, the safety profile of Taltz (ixekizumab) is similar to that of etanercept with rare infectious complications. The clinical effects of targeting Th17 cells through IL-17A neutralization remain an unknown but attractive therapy in BP. The timing of targeting is paramount as prior studies in psoriasis often involve individuals with chronic plaque psoriasis in which there may be a larger percentage of Th17 cells. Therefore, the effects of Taltz (ixekizumab) in BP may be dependent upon the duration of disease prior to the institution of therapy.

The purpose of this study is to determine the effect of Taltz (ixekizumab) on BP patients as assessed by new blister formation, BPDAl, and prednisone usage. IL-17 inhibition with Taltz (ixekizumab) may have a targeted, disease-modifying effect on BP. This study will examine treatment naïve as well as treatment refractory BP. This will allow for the establishment of proper timing and usage of Taltz (ixekizumab) in BP, i.e. treatment naïve (acute onset) and treatment refractory disease (chronic). Additional serological disease markers, some well-established and some exploratory in nature, will be followed to correlate with disease activity.

## **Primary Objectives and Secondary Objectives:**

**Primary Objectives:** The primary objective is to test the effect of Taltz (Ixekezumab) in the treatment of BP as assessed by cessation of blister formation. The primary endpoint of the study will be to determine the median time from first dose of Taltz (Ixekezumab) to cessation of new blisters.

**Secondary Objectives:** The secondary objectives will examine the efficacy of Taltz (Ixekezumab) by ancillary measures including BPDAl and prednisone use. Additionally, we aim to determine possible serological

predictors of response of BP to Taltz (Ixekizumab) and to assess the safety of Taltz (Ixekizumab) in BP patients.

**Exploratory Objectives:** Based upon prior published research, we will examine possible predictors of response using multiplex cytokine and RNA analysis. Samples will be stored at Mayo Clinic for future research.

### **Research Design:**

This is a single center, exploratory, open-label, single-arm design study of 12 patients with BP. Treatment naïve and treatment refractory patients with BP will be treated with Taltz (Ixekizumab). Patients who are non-responders, to physician choice standard of care, will undergo a washout period and will be enrolled in the study. The washout period is 2 weeks for systemic non-immunosuppressive agents, topical steroids, and topical calcineurin inhibitors. A 4-week washout period will be used for systemic systemic immunosuppressive agents or 5 half-lives, whichever is longer, and no live vaccines should be administered within 12 weeks of the study drug. ([Table-1](#)) The study consists of 3 epochs: screening/washout period (of at least 1 week and up to 4 weeks), treatment epoch (of 12 weeks from screen/washout), and follow up epoch (of 6 weeks). The screening and washout period will allow for treatment naïve/ new diagnosis BP to undergo evaluation and diagnosis and for treatment refractory to undergo a washout. The total duration of the study will be 18 weeks.

The duration of treatment, 12 weeks, is based upon the maximal efficacy and dosing regimen of Taltz (Ixekizumab) in psoriasis.(7) Although psoriasis and BP are different disease processes, we would expect a response by 12 weeks of treatment. The open-label, single-arm design will allow for the assessment of the effects of Taltz (Ixekizumab) monotherapy in patients with acute and chronic disease in a relatively short time frame and will minimize study costs. This is critical as there may be a significant benefit either earlier or later in the disease course. This design will also allow for more patients to undergo targeted, serological analysis, which will provide in-vivo evidence of the pathogenesis of disease as well as the changes that occur during treatment. The open-label design of this study will have assessment bias on the part of the patient as well as the physician. The single-arm design will not allow for blinded assessment. In order to mitigate these issues, we will be using objective and validated methods of clinical assessment, which should be robust including: new blister formation, BPDAI, and prednisone usage. Additionally, the serological markers, which are secondary endpoints, will be assessed as an unbiased corollary to the primary effects of Taltz (Ixekizumab) on BP patients.

Our laboratory will perform a multiplex cytokine analysis on serum and blister fluid for Interleukin (IL)-6, -17, -22, -23 on an ELISA assay. Similar array based ELISAs will be used for Transforming Growth Factor beta (TGFb) and matrix-metalloprotease-9 (MMP-9) expression. The serum, cell pellet, and blister fluid will be stored per protocol and a single batch of samples from weeks 0, 4, 8, and 12 weeks will be run in parallel and in duplicate at the end of the study. The array-based kits are standardized and the dilutions of the serum and blister fluid will be optimized prior using the ELISA arrays. Additionally, we will perform analysis of RNA levels in the blister and serum. Finally, we will perform RNA analysis on archival biopsy tissue from each subject to correlate with the changes in the blood and serum.

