- Ongoing use of prohibited treatments. Washout periods detailed in [Table-1](#).
- Previous exposure to Taltz (Ixekizumab) or any other biologic drug directly targeting IL-17A or IL-17RA
- Use of any other investigational drugs within 5 half-lives of the investigational treatment before study drug initiation or until the pharmacodynamics effect has returned to baseline, whichever is longer
- Previous use of IL-20 monoclonal antibody
- Pregnant or nursing (lactating) women (pregnancy is defined as the state of a female after conception and until the termination of gestation, confirmed by a positive human chorionic gonadotropin (hCG) laboratory test)
- Women of childbearing potential [Post-menopausal or not of child-bearing potential is defined by: 1 year of natural (spontaneous) amenorrhea or Surgical bilateral oophorectomy (with or without hysterectomy), total hysterectomy or tubal ligation at least 6 weeks ago. Oophorectomy alone must confirmed by follow up hormone level assessment to be considered not of child-bearing potential, defined as all women

physiologically capable of becoming pregnant, unless they are using basic methods of contraception which includes:

- Total abstinence (Periodic abstinence and withdrawal are not acceptable methods of contraception)
- Female sterilization (bilateral oophorectomy with or without hysterectomy), total hysterectomy, or tubal ligation at least 6 weeks before taking study treatment. Oophorectomy alone requires follow up hormone level assessment for fertility.
- Male sterilization (at least 6 months prior to screening). The vasectomized male partner should be the sole partner for that subject.
- Barrier methods of contraception: condom or occlusive cap.
- Use of oral, injected or implanted hormonal methods of contraception or other forms or hormonal contraception that have complete efficacy (failure <1%). (The dose of the contraceptive should be stable for 3 months)
- Active ongoing inflammatory diseases of the skin other than BP that might confound the evaluation of the benefit of Taltz (Ixekizumab)
- Underlying condition (including, but not limited to metabolic, hematologic, renal, hepatic, pulmonary, neurologic, endocrine, cardiac, infectious or gastrointestinal conditions) which, in the opinion of the investigator, significantly immunocompromises the subject and/or places the subject at unacceptable risk for receiving an immunomodulatory therapy

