**Tables:****Table-1: Prohibited treatment**

Prohibited treatments†,‡	Washout period (before Randomization Visit)
Taltz (Ixekizumab)	No prior use allowed
Any biologic drug directly targeting IL-17 or the IL-17 receptor (other than Taltz (Ixekizumab), e.g., brodalumab, secukinumab)	No prior use allowed
Other systemic immunomodulating treatments § [e.g., methotrexate, cyclosporine A, corticosteroids (oral, i.v., intramuscular, s.c., intra-articular, transdermal)  , mycophenolate mofetil, azathioprine ]	4 weeks
Topical treatment that is likely to impact signs and symptoms of BP (e.g., pimecrolimus, tacrolimus)	2 weeks
Live virus vaccinations	6 weeks
Non-immunosuppressive agents (tetracycline antibiotics & niacinamide)	2 weeks
Prohibited regimen of Topical Corticosteroids (TCS)	
TCS on any location on body (including face, scalp and/or genitoanal area)	2 weeks
Non-BP Therapy	Stable period (before Randomization Visit)
Any other treatment known to worsen BP (angiotensin converting enzyme inhibitors & furosemide)	Stable at least 4 weeks before randomization

-subjects may be on up to 20mg of oral prednisone but must be on a stable dose prior to initiation of ixekizumab

† If the prohibited treatment is being used during the study for any indication, the subject must discontinue use of the prohibited treatment if he/she wishes to continue in the study.

‡ In case of undue safety risk for the subject, the subject should discontinue study treatment at the discretion of the investigator/qualified site staff. If the subject received a live virus vaccination during the study, the subject must discontinue study treatment.

§Inhalative CS with only a topical effect (e.g., to treat asthma) are not considered “**systemic** immunomodulating treatments” and are therefore acceptable as co-medication.

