**Table-2: Screening and Visits**

	Screening	Day 0	Week 2	Week 4	Week 6	Week 8	Week 10	Week 12	Week 18
Ixekizumab		X	X	X	X	X	X	X	
Physical Exam	X	X	X	X	X	X	X	X	X
Adverse Event Assessment		X	X	X	X	X	X	X	X
Chest X-ray	X								
BPDAl		X	X	X	X	X	X	X	X
Photographer		X	X	X	X	X	X	X	X
ECG	X								
Venipuncture	X	X		X		X		X	
Serum Pregnancy Test	X								
anti-BMZ autoantibodies	X								
CRP-C reactive protein	X								
anti-BP230 IgG	X	X		X		X		X	
anti-BP180 IgG	X	X		X		X		X	
CMP	X					X			
CBC	X	X		X		X		X	
Quantiferon Gold	X								
Hepatitis B	X								
Hepatitis C	X								
HIV	X								
Coccidioidomycosis	X								
HbA1c	X								
Interleukin 6, 17, 22, 23		X		X		X		X	
TGFb- Transforming growth factor beta		X		X		X		X	
MMP-9 Matrix-metalloprotease-9		X		X		X		X	

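### Table-1, which the washout exclusion relies on, gives 4 weeks for systemic immunomodulators, while the Research Design section requires the longer of 4 weeks and 5 half-lives

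*Combined protocol and SAP*

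**What the plan says.** The Research Design section sets the washout for patients coming off systemic treatment: "A 4-week washout period will be used for systemic systemic immunosuppressive agents or 5 half-lives, whichever is longer" (the repeated word is in the document). It then refers the reader to Table-1.

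In Table-1 the row "Other systemic immunomodulating treatments" gives methotrexate, cyclosporine A, corticosteroids, mycophenolate mofetil and azathioprine as examples, with a washout of 4 weeks. No footnote adds a half-life condition. The one exception is for corticosteroids: "subjects may be on up to 20mg of oral prednisone but must be on a stable dose prior to initiation of ixekizumab". The column is headed "Washout period (before Randomization Visit").

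The exclusion list points to the table: "Ongoing use of prohibited treatments. Washout periods detailed in" Table-1. Its only half-life rule is for a different class: "Use of any other investigational drugs within 5 half-lives of the investigational treatment before study drug initiation".

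The study design paragraph of the Project Overview and the Research Design section both describe a "screening/washout period (of at least 1 week and up to 4 weeks").

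On live vaccines, the Research Design section and the exclusion list both require 12 weeks before study drug. Table-1 requires 6.

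**The concern.** Eligibility is normally checked against the exclusion list and the table it cites. Staff who do that here apply a flat 4 weeks and never meet the half-life condition. The preamble to the exclusion list also tells the investigator not to add exclusions of their own, which makes it less likely that a rule found only in the Research Design section is applied.

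Treatment-refractory patients are one of the two groups the study sets out to enrol, and failure of a systemic immunosuppressant is one of the listed routes in. The Table-1 row is open-ended, and the Introduction names rituximab among the immunosuppressants used in this disease, so agents beyond the listed examples can fall under the 4 weeks.

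A patient dosed on Table-1 alone, after an agent with a long half-life, would be a deviation from the Research Design rule. There could also be carryover from the earlier drug. The study means to describe ixekizumab monotherapy and has no control arm, so carryover could not be separated from the drug's own effect. With 12 patients, each is 1/12, or about 8%, of the data.

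**Working it through.** The plan has no figure of its own to reproduce. The check is a comparison of texts and a break-even.

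**Texts side by side**

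| Item | Research Design | Exclusion list | Table-1 |
|---|---|---|---|
| Systemic immunosuppressives / immunomodulators | longer of 4 weeks and 5 half-lives | refers to Table-1 | 4 weeks |
| Live vaccines | 12 weeks | 12 weeks | 6 weeks |

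The labels differ (immunosuppressive in one place, immunomodulating in the other). The Table-1 examples include agents of the kind the Research Design section describes, and that section cites the table, so both address the same class.

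**Anchor.** Table-1 counts back from a randomization visit. The study has a single arm, and "Table-2: Screening and Visits" lists screening, Day 0 and visits from Week 2 to Week 18, with no such visit. Elsewhere the windows run to the start of study drug: Table-1's own prednisone footnote, the investigational-drug exclusion, and both 12-week live-vaccine statements. Day 0 is therefore used below.

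**Break-even.** Let t be the half-life in days. Research Design requires max(28, 5t) days and Table-1 requires 28. They agree when 5t ≤ 28, that is t ≤ 28/5 = 5.6 days.

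**Shortfall above the break-even** = max(28, 5t) − 28. The documents give no half-lives, so the values of t are assumptions chosen to show the range. The last column, 0.5^(28/t), also assumes first-order elimination.

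| Assumed t (days) | Research Design (days) | Table-1 (days) | Shortfall (days) | Drug left at day 28 |
|---|---|---|---|---|
| 5.6 | 28 | 28 | 0 | 3% |
| 7 | 35 | 28 | 7 | 6% |
| 14 | 70 | 28 | 42 | 25% |
| 21 | 105 | 28 | 77 | 40% |

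For reference, 0.5^5 = 3% remains after five half-lives. Drug remaining is not the same as clinical effect remaining.

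**Live vaccines.** 12 weeks − 6 weeks = 84 − 42 = 42 days. The exclusion list states the 12 weeks itself, so nobody's eligibility changes when that list is applied.

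**Epoch length.** A washout of 5t days exceeds the 28-day maximum for any t above 5.6 if it begins at screening. If the agent was stopped earlier, part or all of the washout is already complete.

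**The case against.** The strongest reply is that the two rules are compatible. A washout that meets the Research Design rule also meets Table-1, and the section stating the longer rule cites the table. A reader might infer that Table-1 licenses earlier dosing. It does not: the Research Design requirement is current text and still applies. What stands against the reply is that the exclusion criterion sends staff to the table alone.

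A second reply is that no named drug has been shown to exceed 5.6 days. That is correct. The documents contain no half-lives, and the values above are not tied to any agent. The row is open-ended, however, and a half-life condition matters only for agents that need more than 4 weeks, which is the case the table leaves out.

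Two further readings are tempting. One is that the randomization wording leaves the washout without an end point, so that it might be counted back from screening. Nothing in the documents equates randomization with screening, and the neighbouring wording points to first dose; it reads as a template leftover. The other is that the 4-week epoch makes a longer washout impossible. That holds only if washout starts at screening, which the text does not require.

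It can also be said that the sponsor may have intended the flat 4 weeks, since it matches the epoch limit. The documents do not settle this. The longer rule is the one stated explicitly as a design requirement, and it better protects the monotherapy aim.

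Finally, the consequences are cushioned. These patients failed their earlier treatment, stable prednisone up to 20 mg/day is allowed, and the study is for estimation only. Blood-count and active-infection exclusions, with infection checks at every visit (Supplemental 3), cover part of the safety side. All of this stands and keeps the severity low.

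**Conclusion.** The mismatch is real and sits in current, operative eligibility text. Counted from first dose, Table-1 is shorter than the Research Design rule for any systemic agent with a half-life above 5.6 days. The shortfall would be 7, 42 or 77 days at assumed half-lives of 7, 14 or 21 days. Whether any of the 12 patients would be affected is unknown. The effect on time to cessation of blisters cannot be quantified from the documents and may be small.

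A reader might go further and infer that the study's results will be biased by carryover, or that recently vaccinated patients will be admitted. The documents support neither: the first needs half-lives and prior treatments that are not given, and the second is prevented by the exclusion list. Severity is low. The reason to act is that the correction is specific and cheap, and it removes an avoidable route to a protocol deviation.

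**What to change.** 1. In Table-1, change the systemic immunomodulating row to the longer of 4 weeks and 5 half-lives, and keep the footnote for stable prednisone up to 20 mg. Because the exclusion criterion cites this table, the half-life rule then becomes part of the exclusion list.
2. In Table-1, change live virus vaccinations to 12 weeks.
3. Replace every randomization anchor with Day 0 (first dose): both Table-1 column headers, the stable-dose cell for treatments known to worsen the disease, and the exclusions on active systemic infection and on latent tuberculosis treatment.
4. In the Project Overview's study design paragraph and in Research Design, state that the screening/washout epoch may extend beyond 4 weeks, after consent, when 5 half-lives requires it, and that time off an agent already stopped for clinical reasons before screening counts. The consent condition matters because the inclusion criteria require consent before any study activity, so a drug should not be stopped for the study before then.

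The cost is two cells, the anchor wording in five places, and a clarifying statement in two sections. Endpoints, sample size and analysis do not change. The stated 18 weeks is the 12 treatment weeks plus the 6 follow-up weeks, so a longer washout does not alter it. The practical downside is a longer wait before dosing for a few refractory patients.
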